6 STATISTICAL ANALYSES

6.1 PARTICIPANT DISPOSITION

Participant disposition (all participants) will be summarized before and after the 2020 voluntary dose pause separately including participants enrolled, participants in each analysis population/set, participants who completed the study, participants who discontinue study drug with primary reasons for study drug discontinuation, participants who withdraw prior to completing the study with primary reason for withdrawal, and period of clinical hold or voluntary dose pause for each participant.

6.2 DEMOGRAPHICS AND BASELINE CHARACTERISTICS

Demographics and baseline disease characteristics will be summarized for the safety analysis set 1 and safety analysis set 2. Demographics will include age, age group, gender, race, ethnicity, height, weight, body mass index (BMI), and region. Baseline hemophilia disease characteristics will be reported from parent study TDR14767(ALN-AT3SC-001) and will include hemophilia type, biological phenotype, historical ABR based on 6-month bleed history prior to parent study entry and historical number of hemophilia clinic visits.

6.3 EFFICACY

Bleeding event definitions

A bleeding episode is defined as any occurrence of hemorrhage that may require administration of BPA infusion or factor concentrates. Bleeding episodes sustained during sports and recreation will be counted as traumatic bleeding episodes.

Bleeding or any symptoms of bleeding at the same location that occur within 72 hours of the last injection used to treat a bleed or 72 hours after an untreated bleed at that location will be considered a part of the original bleeding event and will count as one bleeding episode. Any bleeding symptoms that begin more than 72 hours from the last injection used to treat a bleed or 72 hours after an untreated bleed at that location will constitute a new bleeding event.

The following definitions of bleeding event types, based on consensus opinion of International Society on Thrombosis and Haemostasis (ISTH), will apply:

Traumatic bleed: caused by a known injury or trauma, including sports and recreation

Spontaneous bleed: that occurs for no apparent or known reason

Joint bleed: an unusual sensation in the joint (“aura”) in combination with either of

- increasing swelling/warmth on the skin over the joint
- increasing pain
- progressive loss of range of motion

- progressive difficulty in using the limb.

Muscle bleed: pain, swelling and loss of movement over the affected muscle group.

A target joint is defined as a joint where 3 or more spontaneous bleeding events occur within a consecutive 6-month period has occurred; if ≤ 2 bleeding events occur in a joint within a consecutive 12-month period the joint will be excluded from target joint.

Traumatic bleeds that occur in different locations simultaneously (same date/time) in the same participant will be considered as one bleeding episode. Spontaneous bleeds that occur simultaneously (same date/time) in different locations in the same participant will be considered as separate bleeds.

Efficacy analysis will focus on observed data as collected, unless otherwise specified. Only bleeding episodes that are treated with BPA/factor will be included in the primary analysis of endpoints evaluating bleeding; however additional analyses will be performed which will include all bleeds, both treated and untreated.

Definition of analysis period

The analysis periods will be defined separately before and after the volunteer dose pause.

The original dose and regimen:

- Onset period: The onset period is defined as the period of time consisting of the first 28 days: Treatment Day 1 to Treatment Day 28 (of TDR14767(ALN-AT3SC-001) and LTE14762) (see above - definition of “Treatment Day”); this is the period of time during which the AT lowering capacity of fitusiran is increasing but has not yet reached therapeutic levels.
- Efficacy period 1: The efficacy period 1 is defined as Treatment Day 29 to earlier of End of study date before the dose pause or the last fitusiran administration date before the dose pause + 28 days, whichever comes first.
- Treatment period 1: The treatment period 1 is defined to be the onset period plus the efficacy period 1.

The revised dose and regimen:

- Dose adjustment period: The dose adjustment period is defined as the dose re-start Day 1 to the earlier of dose re-start Day 168 or the end of study.
- Efficacy period 2: The efficacy period 2 is defined as the dose re-start Day 169 to the end of study visit
- Treatment period 2: The treatment period 2 is defined to be the dose adjustment period plus the efficacy period 2.

All the analysis periods will exclude the period of following intercurrent events to avoid confounding of treatment effect for the primary efficacy analysis based on On-Treatment Strategy:

Intercurrent events:

I. “Dose interruption periods”:

- a. Gap between TDR14767(ALN-AT3SC-001)/ LTE14762 study >28 days and skips at least two doses in the gap: Exclude events occurring on dates starting from the date of the last dose in 001 +29 days to the date of first dose in LTE14762 +28 days and gap duration >84 days.
- b. Clinical hold/dose pause period during LTE14762 study: Exclude events occurring on dates starting from the date of the last dose before dose interruption +29 days to the date of dose resumption +28 days and on-hold duration > 84 days.
 - Dose hold in 2017: The last dose before dose interruption is defined as the last fitusiran administration before 2017 [REDACTED]. The first dose after dose resumption is defined as the first fitusiran administration after 2017 [REDACTED].
 - Voluntary dose pause in 2020: The last dose before dose interruption is defined as the last fitusiran administration before 2020 [REDACTED]. The first dose after dose resumption is defined as the first fitusiran administration after 2021 [REDACTED].
- c. Missing two consecutive doses in LTE14762 (eg, a participant skips at least two consecutive scheduled doses): If participant under Q2M regimen before the dose interruption, then exclude events occurring on dates starting from the date of the last dose before the dose interruption + 57 days to the date of the dose resumption + 56 days. If participant under QM regimen before the dose interruption, then excluded events from the date of the last dose before the dose interruption + 29 days to the date of the dose resumption + 28 days. The missing two consecutive doses will be considered separately before and after the dose pause in 2020.
- d. Fitusiran treatment discontinuation in LTE14762: Exclude events occurring on any dates starting from the date of the last dose +29 days if the last dose regimen is QM (ie, until the end of the study.) If the last dose regimen is Q2M, then the start date of this intercurrent event should be last dose + 57 days.

II. Perioperative period of major surgery and major trauma is defined as the day of the surgery or trauma through the final day on which supplemental hemostatic or antithrombotic treatments are administered as part of the perioperative treatment plan.

III. Perioperative period of minor surgery is defined as the perioperative period of surgery as defined for major surgery (see above) or to 72 hours from the end of surgery, whichever is later.

IV. Period of antithrombin treatment defined as the first day of antithrombin treatment through the final day on which antithrombin or other anticoagulant therapies are administered +5 half-lives.

V. After treatment with emicizumab.

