5.2 GENERAL METHODS

Both efficacy and safety analysis under the original and revised dose regimens will be analyzed separately, unless otherwise specified. The data collected during the 2020 voluntary dose pause will be analyzed along with the pre-pause data.

A significant dose is defined as any single dose of fitusiran that is greater than or equal to 20 mg. Before the voluntary dose pause, the analysis period for efficacy endpoints starts from the date of first significant dose up to the earlier of 2020 voluntary dose pause date or the last day of study follow-up. For safety endpoints, the analysis will be performed based on LTE14762 study period data only up until the dose restart date. Date of first significant dose in the TDR14767(ALN-AT3SC-001) and LTE14762 study/studies will be designated as Treatment Day 1; there will be no Treatment Day 0. Participants who receive doses (either weight-dependent or weight-independent) of at least 20 mg but less than 75 mg will be “classified” as “50 mg” participants, while participants receiving doses of greater than or equal to 75 mg will be “classified” as “80 mg” participants (except PK analysis in which actual dose on Day of PK sample collection will be used). However, for purposes of efficacy and safety analyses and summaries in the final CSR report for the LTE14762 study, the classification of each participant under the original dose and regimen will be according to the fixed dose to which they are eventually taken by the end of the LTE14762 study original dose period. For example, participants who received a 50 mg dose in TDR14767(ALN-AT3SC-001) or LTE14762 and then were switched to 80 mg dose at some point in time during the LTE14762 study, are classified in the LTE14762 study as “80 mg” participants (except for PK analyses). Treatment after the volunteer dose pause will be treated as each participant’s treatment sequence.

[figure not shown]
Treatment Days under the original dose and regimen will be calculated as evaluation date – first significant dose date +1 and pre-treatment days will be calculated as evaluation date – first significant dose date. (The pre-treatment day formula applies when evaluation date < first significant dose date; ie, for example, there will be pre-treatment Days ... -3, -2, -1, then treatment Day 1, 2, 3, 4, ...; there is no “pre-Treatment Day 0” nor is there any “Treatment Day 0”).

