6.3.1 Analysis of long-term durability and efficacy

6.3.1.1 Annualized bleeding rate

The ABR efficacy analysis will include all bleeding events occurring in the efficacy period. The ABR will be annualized for each participant using the following formula:

$$\text{Annualized bleeding rate (ABR)} = \frac{\text{total number of bleeding events}}{\text{total number of days in the respective period}} \times 365.25$$

The primary efficacy analysis will consist of the ABR results based on the “on-treatment strategy” during the efficacy period (efficacy period as strictly defined in [Section 6.3](#) above, excluding the periods of intercurrent events). The “on-treatment strategy” analysis will also be performed for the onset period and the treatment period. The “treatment policy strategy” analysis, will be performed for the treatment period only, and will consist of the ABR calculations applied to *all* (treated) bleeds (even including surgery periods), taking place during the analysis period of interest only excluding the gap between TDR14767(ALN-AT3SC-001) and LTE14762 where the bleeds were not collected. ABR will be estimated (with 95% CI) using a negative binomial model adjusted by TDR14767(ALN-AT3SC-001) study baseline ABR. No imputations of missing data will be performed in the ABR analyses. The ABR analysis under the original dose and regimen will be performed for the entire efficacy period 1 and also for the treatment period 1 and onset period (for the “on-treatment strategy”), as well as by year for the treatment period 1 (both on-treatment and treatment policy strategies) in order to demonstrate the durability of the prophylactic maintenance. Model based ABR will be provided when there are at least 3 participants in the group and model converges for by-year analysis. Also, additional analyses will be performed including all bleeds, both “treated” and “untreated”.

ABR under the revised dose and regimen after the dose pause for treated bleeding events and all bleeding events during the dose adjustment period, efficacy period 2 and treatment period 2 based on on-treatment strategy will be analyzed respectively. ABR for treated bleeding events during the treatment period 2 will also be summarized based on on-treatment strategy every 6 months. Similar ABR analysis during treatment period 2 based on treatment policy (ignoring all intercurrent events) will be performed as well.

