6.8.1 Study drug exposure

Duration of exposure (years) and the number of study drug doses used from Treatment Day 1 in the TDR14767(ALN-AT3SC-001)/LTE14762 under the original dose and regimen will be summarized descriptively, where duration of exposure (days) = date of the last dose of study drug – the date of the first significant dose of study drug + 28 days excluding the gaps between TDR14767(ALN-AT3SC-001)/LTE14762 and dose suspension in LTE14762. Duration of exposure and the number of study drug doses in LTE14762 study will be summarized similarly.

Duration of exposure under the revised dose and regimen will be summarized. If participant had the last dose under the Q2M dose frequency, the duration (days) = date of the last dose of fitusiran – the date of the first dose of fitusiran under the revised dose and regimen + 56 days. If participant had the last dose under the QM dose frequency, the duration (days) = date of the last dose of fitusiran – the date of the first dose of fitusiran under the revised dose and regimen + 28 days.

The overall duration of exposure regardless of revised dose from the first significant dose and/or from the first dose in the LTE14762 study until the end of study may also be summarized as needed. The planned dose intermittent period ([Table 4](#)) will be excluded from the overall duration of exposure.

Table 4 – Definition of planned dose intermittent periods

	Start date	End date	Note
Gap between parent and extension study	Last fitusiran dose date in parent study + 29 days	First fitusiran dose date in extension study – 1	If duration < 14 days, then no gap between the 2 studies.
2017 dose suspension	Last fitusiran dose before 01SEP2017 + 29 days	First fitusiran dose after 01SEP2017 – 1	If duration < 14 days, then no dose suspension period should be excluded.
2020 dose suspension	Last fitusiran dose date before 31Oct2020 + 29 days	First fitusiran dose after 26Jan2021 – 1	If duration < 14 days, then no dose suspension period should be excluded

Note: Duration is calculated as end date – start date +1 for each dose intermittent periods.

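### The on-treatment ABR drops the parent-to-extension gap only above 84 days, so any uncollected days in shorter gaps count as bleed-free time

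*SAP*

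**What the plan says.** SAP 5.2 starts the efficacy clock at the first dose of at least 20 mg, in either study: "Date of first significant dose in the TDR14767(ALN-AT3SC-001) and LTE14762 study/studies will be designated as Treatment Day 1". SAP 6.3 then runs the main period on from there: "The efficacy period 1 is defined as Treatment Day 29 to earlier of End of study date before the dose pause" (or 28 days after the last pre-pause dose, if sooner). For such participants who were first dosed in the parent study, this period spans the roll-over.

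Time leaves the on-treatment analysis only through listed events: "All the analysis periods will exclude the period of following intercurrent events to avoid confounding of treatment effect". Item I.a covers the roll-over. It applies to a gap between the two studies described as "LTE14762 study >28 days and skips at least two doses in the gap", and it removes events from 29 days after the last parent dose "to the date of first dose in LTE14762 +28 days and gap duration >84 days". Items I.b to I.d are confined to the extension study, and II to V concern surgery, trauma, antithrombin treatment and emicizumab.

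Two other places treat the same interval differently:

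- SAP 6.3.1.1 counts all treated bleeds under treatment policy, "only excluding the gap between TDR14767(ALN-AT3SC-001) and LTE14762 where the bleeds were not collected". No minimum length is given.
- SAP 6.8.1, Table 4, takes the gap out of exposure from last parent dose +29 days to first extension dose -1 day, unless it is short: "If duration < 14 days, then no gap between the 2 studies".

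ABR divides the bleed count by the "total number of days in the respective period", with no imputation.

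**The concern.** Item I.a looks designed to remove time when drug effect has worn off, and a length threshold can be defended for that purpose. Missing ascertainment is a separate problem, and it does not begin at day 85. A day on which no bleed could be recorded adds to the denominator and can add nothing to the numerator.

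Followed as written, the on-treatment denominator keeps days that the treatment-policy denominator drops, although on-treatment is meant to be the narrower of the two. Some of those days are also not exposure under Table 4. At stake are the primary efficacy ABR, the by-year ABR that SAP 6.3.1.1 uses to show durability, and the maximum bleed-free duration in SAP 6.3.1.2. An interval that spans the gap is lengthened by the uncollected days, and an unrecorded bleed would have split it.

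**Working it through.** The documents state no ABR, event count or gap length for this point, so there is no figure to reproduce. The check is how far the rule can move an ABR.

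**Inputs**

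- ABR = bleeds / days × 365.25 (SAP 6.3.1.1).
- Extension enrolment began 08-Oct-2015 (SAP 2.5), the parent study ended 20 July 2017 (SAP 2.1), and the 2020 pause date is 31 Oct 2020 (SAP Table 4). Follow-up T therefore runs from about 1,199 days (20 July 2017 to 31 Oct 2020, 3.3 years) to 1,850 days (08-Oct-2015 to 31 Oct 2020, about 5 years).
- D, the dose-to-dose gap in days, is an assumption, varied over the range that the rule leaves in.

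**Days left in.** The days from last parent dose +29 to first extension dose -1 number (D - 1) - 29 + 1 = D - 29.

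- D = 30: 1 day stays in.
- D = 43: 14 days, the point at which Table 4 first recognises a gap. For D = 30 to 42, Table 4 itself would keep 1 to 13 days.
- D = 84: 55 days stay in, and I.a removes nothing.
- D = 85: I.a applies and removes last dose +29 to first dose +28, which is D + 28 - 29 + 1 = 85 days.

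**Effect on ABR.** If u days in a period of T days were uncollected, reported ABR divided by ABR over collected days is (T - u)/T, so the understatement is u/T whatever the true rate.

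| Uncollected days u | T = 365 | T = 730 | T = 1,199 | T = 1,850 |
|---|---|---|---|---|
| 1 (D = 30) | 0.3% | 0.1% | 0.1% | 0.1% |
| 14 (D = 43) | 3.8% | 1.9% | 1.2% | 0.8% |
| 28 (D = 57) | 7.7% | 3.8% | 2.3% | 1.5% |
| 55 (D = 84) | 15.1% | 7.5% | 4.6% | 3.0% |

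The 365-day column stands for one year of the by-year analysis. A prompt roll-over after three monthly parent doses puts the gap in year 1. The 730-day column shows an earlier discontinuation. T ignores other exclusions such as the 2017 hold, which would shorten it and raise the percentages.

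**The undefined term.** The table takes gap duration as dose-to-dose. If it were measured as in Table 4, D - 29 could reach 84, so D could reach 113 and 84 days could stay in: 84/1,850 = 4.5%, 84/1,199 = 7.0%, 84/365 = 23.0%. The SAP does not say which is meant.

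**Who is affected.** SAP 5.10 says a first significant dose in the parent study could occur only in Parts C and D. Protocol 1.3.3 lists 15 Part C patients at 0.45 mg/kg or above or 80 mg, and 17 Part D patients, 32 in all. How many of them rolled over, and after what gap, is not stated.

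**The case against.** The strongest reply is that no affected participant is shown. Protocol 3.1 expected Parts C and D to roll over about one month after their third dose, which leaves almost no uncovered days. A gap between doses is also not necessarily a gap in observation. SAP 2.1 required completion of the parent-study visits, the protocol expects some assessments to overlap the two studies, and parent follow-up may have recorded bleeds after the last dose. Protocol 9.1.1 asks for hemophilia history between the studies, including bleeds, and the SAP's remark on non-collection can be read as limiting its exclusion to time that was in fact uncollected. All of this stands against the size. None of it repairs the rule: the SAP has no step that brings that history into the ABR, and I.a tests length and skipped doses, not whether bleeds were recorded.

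Three stronger readings are tempting and are not supported:

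- A reader might infer that the primary ABR is understated by 5% to 15%. Shares of that order belong to a single year, and the by-year analysis uses treatment period 1, not the primary efficacy period. The primary model estimate also includes participants whose gap precedes Treatment Day 1, which dilutes any effect.
- A reader might infer that the rule favours the durability claim. A low year 1 makes later years look relatively worse. By-year ABR is also planned under treatment policy, which excludes the gap.
- A reader might take every day from 29 to 84 as unobserved. The documents do not establish that.

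It is also fair that the study's primary objective is safety and its analyses are mainly descriptive.

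**Conclusion.** The point holds as an error in the rule, with a small and unproven effect. For participants first given at least 20 mg in the parent study, with a dose-to-dose gap of about 30 to 84 days, any uncollected days stay in the primary on-treatment denominator while treatment policy drops them. The direction is downward for ABR and, where the spanning interval is the longest, upward for maximum bleed-free duration.

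On the dose-to-dose reading, the size is near zero for a one-month roll-over, at most roughly 3% to 5% of a participant's ABR over 3.3 to 5 years, and up to about 15% of a year-1 ABR, where it distorts the comparison between years. These ceilings assume that all 55 days were uncollected. They are shares for one participant, not bias in the pooled estimate. The change is worth making because the two strategies contradict each other on the same days and the correction is cheap.

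**What to change.** - Under both strategies, remove from numerator and denominator every day between the studies on which bleeds were not collected, whatever the gap length. Apply neither the 84-day threshold nor Table 4's 14-day threshold; the latter would keep up to 13 such days.
- Keep the >84-day rule only as a further on-treatment exclusion for lost drug effect, including the 28 days after resumption.
- Define gap duration: dose-to-dose, or from last parent dose +29 days.
- Reconcile SAP 6.3.1.1 with protocol 9.1.1. If bleeds in the gap were captured as hemophilia history, include both the bleeds and the days.
- Carry the same days through to bleed-free duration.

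The cost is SAP wording and a small derivation change, with no new data collection. The reported ABR may rise slightly.

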6.3.1 Analysis of long-term durability and efficacy

6.3.1.1 Annualized bleeding rate

The ABR efficacy analysis will include all bleeding events occurring in the efficacy period. The ABR will be annualized for each participant using the following formula:

$$\text{Annualized bleeding rate (ABR)} = \frac{\text{total number of bleeding events}}{\text{total number of days in the respective period}} \times 365.25$$

The primary efficacy analysis will consist of the ABR results based on the “on-treatment strategy” during the efficacy period (efficacy period as strictly defined in [Section 6.3](#) above, excluding the periods of intercurrent events). The “on-treatment strategy” analysis will also be performed for the onset period and the treatment period. The “treatment policy strategy” analysis, will be performed for the treatment period only, and will consist of the ABR calculations applied to *all* (treated) bleeds (even including surgery periods), taking place during the analysis period of interest only excluding the gap between TDR14767(ALN-AT3SC-001) and LTE14762 where the bleeds were not collected. ABR will be estimated (with 95% CI) using a negative binomial model adjusted by TDR14767(ALN-AT3SC-001) study baseline ABR. No imputations of missing data will be performed in the ABR analyses. The ABR analysis under the original dose and regimen will be performed for the entire efficacy period 1 and also for the treatment period 1 and onset period (for the “on-treatment strategy”), as well as by year for the treatment period 1 (both on-treatment and treatment policy strategies) in order to demonstrate the durability of the prophylactic maintenance. Model based ABR will be provided when there are at least 3 participants in the group and model converges for by-year analysis. Also, additional analyses will be performed including all bleeds, both “treated” and “untreated”.

ABR under the revised dose and regimen after the dose pause for treated bleeding events and all bleeding events during the dose adjustment period, efficacy period 2 and treatment period 2 based on on-treatment strategy will be analyzed respectively. ABR for treated bleeding events during the treatment period 2 will also be summarized based on on-treatment strategy every 6 months. Similar ABR analysis during treatment period 2 based on treatment policy (ignoring all intercurrent events) will be performed as well.

The ABR primary analyses described above will be performed again on the PP population to support long-term efficacy of fitusiran and robustness of result. If per-protocol population is the same set of participants as the safety population, then analysis based on safety population will be provided only.

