3.2 ENDPOINTS

3.2.1 Efficacy endpoints

Annualized bleeding rate (ABR) during the efficacy period

Annualized spontaneous bleeding rate during the efficacy period

Annualized joint bleeding rate during the efficacy period

Time intervals between bleeding events

Annualized weight-adjusted consumption of FVIII, FIX and BPA

Quality of life (QoL) measured by EuroQol 5-dimension 5-level (EQ-5D-5L) score

QoL measured by Haem-A-QoL score.

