We also define Study Days in the LTE14762 study as the number of days from first significant dose in LTE14762 and calculate similarly as the Treatment Days. For participants who received first significant dose in LTE14762, the Study Days is the same as the Treatment Days.

For participants under the revised dose and regimen, both efficacy and safety data will be analyzed from the dose re-start Day 1 up until the last day of study follow-up.

Treatment day after the dose re-start will be calculated as evaluation date – first dose date after dose re-start + 1 (days). It should be not applicable for assessments before the dose re-start. A summary of study periods and start day in analysis is outlined in [Figure 1](#)

Figure 1 Study periods and analysis start day summary

	Original dose and regimen	2017 clinical hold/2020 voluntary dose pause	Revised dose and regimen
Efficacy analysis	Starts from first significant dose of fitusiran in TDR14767(ALN-AT3SC-001) or LTE14762 and in terms of treatment days.	Starts from the 29th days after last dose date before the hold/pause	Starts from first dose date of revised dose and regimen and in terms of treatment days
Safety analysis	Starts from first significant dose of fitusiran in LTE14762 and in terms of study days	Starts from the day after last dose date before the hold/pause and in terms of study days	Starts from first dose date of revised dose and regimen and in terms of study days

Summary statistics will be reported by analysis visits defined in [Section 5.10](#) below. Unless otherwise noted, tables under both the original and revised dose regimens will be presented by hemophilia type, inhibitor type and overall. Participants who received a significant dose in TDR14767(ALN-AT3SC-001) will be considered as a subgroup in the analysis under the original dose and regimen. Details will be specified in the [Section 6.11](#).

Categorical data summary will include the number and percentage of participants within each category, with a category for missing data. Continuous data summary will include descriptive statistics - the number of participants, mean, median, standard deviation (SD), first quartile (Q1), third quartile (Q3), minimum, and maximum. The precision of the measurement for each continuous variable will be used to determine the number of decimal places to present in tables, figures and derived listings. Minimum and maximum values will be reported with the same

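### The on-treatment by-year ABR meant to show durability counts the 28 onset days in Year 1, which can raise the year that later years are naturally compared with

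*SAP*

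**What the plan says.** SAP 6.3 divides time under the original regimen in two. The onset period is "the period of time consisting of the first 28 days: Treatment Day 1 to Treatment Day 28", during which "the AT lowering capacity of fitusiran is increasing but has not yet reached therapeutic levels". What follows is the efficacy period: "The efficacy period 1 is defined as Treatment Day 29 to earlier of End of study date before the dose pause", or 28 days after the last pre-pause dose if that comes first. The two are then joined again: "The treatment period 1 is defined to be the onset period plus the efficacy period 1".

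The time axis is set in SAP 5.2, where the efficacy analysis "Starts from first significant dose of fitusiran in TDR14767(ALN-AT3SC-001) or LTE14762 and in terms of treatment days". The endpoint in SAP 3.2.1 is "Annualized bleeding rate (ABR) during the efficacy period". Protocol 10.2.3 likewise starts counting bleeds four weeks after the first dose.

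SAP 6.3.1.1 makes the on-treatment ABR over the efficacy period the primary efficacy analysis. It also runs the ABR "by year for the treatment period 1 (both on-treatment and treatment policy strategies) in order to demonstrate the durability of the prophylactic maintenance".

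Under the on-treatment strategy, intercurrent events I.a to I.c in SAP 6.3 remove time through 28 days after resumption. This applies after a parent/extension gap or a hold of more than 84 days, and after two consecutive missed monthly doses. Onset itself is not on the list of intercurrent events. Under the treatment-policy strategy for this period, the only time removed is the gap between the two studies.

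**The concern.** The by-year table is about maintenance of effect, but its first year contains four weeks that the SAP sets apart because the effect has not been established. Onset occurs once, at the start, so only Year 1 carries it. In the on-treatment version, comparable build-up time after the longer interruptions is taken out wherever it falls. Year 1 and later years are therefore not like for like.

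A reader judging durability will naturally compare later years with Year 1. If bleeding is more frequent during onset, Year 1 is set too high. A real increase in maintenance bleeding could then look flat, and a steady course could look like improvement.

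**Working it through.** The plan gives no bleed rates, durability margin or power figure, so there is nothing of its own to reproduce. The check uses its definitions.

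**Inputs**
- Onset: 28 days, once per participant (SAP 6.3).
- Annualising constant: 365.25 (SAP 6.3.1.1).
- R, the onset bleed rate divided by the maintenance rate: assumed, and varied.
- Y, on-treatment days in Year 1: 365.25 if nothing is excluded.

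**Step 1. Share of Year 1.** 28/365.25 = 7.7%.

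**Step 2. Inflation of Year 1.** With maintenance rate m, the Year 1 rate is [28Rm + (Y-28)m]/Y. Relative to m this is 1 + 28(R-1)/Y. A true later-to-maintenance ratio of 1.30 is displayed as 1.30 divided by that factor.

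| R | Year 1 / maintenance (Y=365.25) | A true +30% is displayed as |
|---|---|---|
| 0.5 | 0.96 | 1.35 |
| 1 | 1.00 | 1.30 |
| 2 | 1.08 | 1.21 |
| 3 | 1.15 | 1.13 |
| 5 | 1.31 | 0.995 |

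With no true change, R=5 would display 1/1.307 = 0.77, an apparent fall of 23%. If R is below 1 the bias reverses.

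**Step 3. A shorter Year 1.** If exclusions fall in Year 1, onset weighs more. At an assumed Y of 180 days its share is 28/180 = 15.6%, and the factors are 1.16, 1.31 and 1.62 for R=2, 3 and 5. The documents do not say how often this would happen.

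**Step 4. With sampling noise.** A simulation used 34 participants (the 13 and 21 in Protocol 1.3.3), an assumed maintenance ABR of 1.5, gamma-distributed participant rates with dispersion 1, and a true 30% rise. The later year looked no worse than Year 1 in 16% of runs at R=2, 27% at R=3 and 53% at R=5. With Year 1 started on Day 29, the figure was 8 to 9% at all three values of R.

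**Step 5. Is an onset-free Year 1 available elsewhere?** SAP 6.3.1.1 also plans the ABR for the whole of efficacy period 1 and for onset alone, but neither is by year. Bleed-free duration (6.3.1.2) covers each efficacy period as a whole. Section 6.5 compares ABR before and after the 2017 hold, not by year. So no planned output gives one.

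**Step 6. The treatment-policy version.** The 2017 hold stays in. If hold time also bleeds at R times the maintenance rate, a hold of h days raises its year by h(R-1)/365.25. For an assumed h=60 and R=3, that year is 1.33 against 1.15 for Year 1, a ratio of 1.15, so an unchanged course would look 15% worse. The cut date of 1 September 2017 (SAP 6.8.1) is Day 695 counted from the first enrolment on 8 October 2015. That is Year 2 if Treatment Day 1 was close to enrolment, and it may be an earlier year for later entrants. The direction is therefore not fixed.

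**The case against.** The strongest reply is that R is unknown and the documents point to a modest value. Protocol 5.3 expects most patients to have AT at or below 60% as early as Day 7, and 94% to have more than 50% lowering by Day 14, so much of onset has partial effect. Protocol 5.2 bars factor prophylaxis only after Day 7. Treatment Day 1 is the first dose of at least 20 mg, so some participants may reach it with AT already lowered by smaller doses: the expected starting dose of 0.225 mg/kg (Protocol 6.5) is below 20 mg for anyone under 20/0.225 = about 89 kg. All of this stands. It limits the likely size but does not make onset time informative about maintenance.

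It is also fair that the analyses are primarily descriptive, that the SAP names no reference year and no trend test, that Years 2 onward can be compared with each other, and that the on-treatment onset ABR is reported separately. Comparison with Year 1 is an inference from the treatment-day axis and the stated purpose. SAP 2.6 says the treatment period was defined for consistency with other fitusiran studies, so the choice looks deliberate. That is a reason to keep the version as supportive, not to make it the only one.

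A reader might infer that later years contain no onset-like time at all. The documents do not support that: gaps or holds of 84 days or less that do not involve two consecutive missed doses leave their recovery time in. The 56-day rule for dosing every two months is also not relevant here, because that regimen began after treatment period 1 had ended.

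**Conclusion.** The point holds for the on-treatment by-year ABR. Year 1 includes 28 days that the SAP regards as pre-therapeutic, while most comparable time after later interruptions is removed. Year 1 is inflated by about 8% at R=2, 15% at R=3 and 31% at R=5, assuming a full Year 1 and an onset rate above the maintenance rate. At R=1 there is no effect. A later rise of the same size could appear flat. The primary ABR on efficacy period 1 is not affected.

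A stronger reading, that both by-year tables are biased towards durability, is not supported. The treatment-policy table also counts the 2017 hold and the re-onset after it, which can push the affected year up. Taking only onset out of that table would break the strategy's definition and could tilt it the other way. Nor do the documents show that a loss of effect would in fact be hidden, since that depends on rates they do not give.

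**What to change.** In SAP 6.3.1.1, specify the on-treatment by-year ABR on efficacy period 1, with Year 1 starting on Treatment Day 29 (Year 1 = Days 29 to 393, Year 2 = Days 394 to 758, and so on). Show the already planned onset-period ABR as its own row in the same table. The Year 1 factor is then 1.00 for any R, and the table matches the efficacy-period endpoint in SAP 3.2.1 and the four-week start in Protocol 10.2.3.

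Keep the on-treatment by-year version on treatment period 1 as supportive, for comparison with other fitusiran studies. Leave the treatment-policy by-year analysis as defined, with a note that it includes the 2017 hold and is not a clean durability comparison.

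The cost is a sentence of SAP text, a short note and a changed start day in the program, with no new data. The downside is that Year 1 ABR may be slightly lower, and the main by-year table will differ from the treatment-period version because its years are shifted by 28 days.
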